5.1 Prohibited treatment

Use of the treatments displayed in [Table 5-1](#) is NOT allowed after the start of the washout period unless specified otherwise below.

Live vaccines should not be given until 12 weeks after last study treatment administration.

Table 5-1 Prohibited medications

Prohibited treatments	Prohibition ¹ /Washout period before randomization ²	Action to be taken
Any immunomodulating biologic drugs, including but not limited to TNFalpha inhibitors or other biologic drugs targeting IL-17 or IL-17 receptor*	Never	Discontinue study medication
Any cell-depleting therapies including but not limited to anti-CD20 or investigational agents*	Never	Discontinue study medication
cDMARD (e.g. MTX) including apremilast, tofacitinib*	Never	Discontinue study medication
Any investigational treatment other than study medication or participation in any interventional trial	4 weeks or 5 half-lives (whichever is longer)	Discontinue study medication
Unstable dose of NSAIDs (including selective COX-2 inhibitors) and/or paracetamol/acetaminophen	2 weeks	Reduce dose as soon as possible, back to baseline dose. Dose decreases after randomization are allowed within the first 14 weeks Dose increases are only allowed after Week 14. All dose changes must be recorded
Analgesics other than NSAIDs, paracetamol/acetaminophen and low strength opioids PRN	2 weeks	Discontinue the forbidden medication. All medications must be recorded
High potency opioids	12 weeks	Discontinue study medication
Systemic corticosteroids	12 months	Discontinue study medication
Local steroid injections in the shoulder (until Week 14)	8 weeks and not more than 3 injections	Discontinue study medication
Intramuscular steroid injection	8 weeks	Discontinue study medication
Fluoroquinolone	8 weeks	Discontinue study medication

Prohibited treatments	Prohibition ¹ /Washout period before randomization ²	Action to be taken
Shock wave therapy	8 weeks	Discontinue study medication
Live vaccinations	6 weeks	Discontinue study medication
Platelet rich plasma injections	12 months	Discontinue study medication
Oral or topical retinoids	12 weeks	Discontinue study medication

* These agents fall under the category of biologic immunomodulators and are prohibited medications.

¹ Never = medication is prohibited from any time point prior to study start and up to and including follow-up visit

² period in weeks refers to washout of prohibited medications during screening counted from randomization visit
Administration of these agents requires study discontinuation.

6 Treatment

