3.2 Rationale for study design

The study design addresses the primary objective of determining the efficacy of secukinumab in improving signs, symptoms and structure in patients with overuse rotator cuff tendinopathy. The study will enroll patients with inadequate response (determined by a VAS pain score ≥ 4) to physiotherapy or NSAIDs/acetaminophen or intolerance to NSAIDs/acetaminophen, using a double-blinded, randomized, parallel group design to minimize bias. At the time of inclusion, patients can be steroid-naïve or have inadequate response or intolerance to local steroid injection in the tendon, but last steroid therapy must have been >8 weeks prior to randomization. Patients must be naïve to IL-17 inhibition therapy.

The patient population with rotator cuff tendinopathy was chosen, as this is one of the most frequent tendinopathies. Moreover, the clinical evidence for an IL-17 connection has so far only been shown for rotator cuff tendinopathy and has not been investigated for other tendinopathies (Millar et al 2017).

Currently, no Health Authority guideline exists for developing drugs for the overuse tendinopathy indication. The 14-week endpoint is chosen to allow the last injection at 12 weeks to take effect.

The study uses validated Patient Reported Outcome (PRO) questionnaires including indices of signs, symptoms and physical function. The PROs used have been chosen based on their validity, reliability and specificity. The different PROs have different recall times, 1 week, 24 hours, and a moment in time. One is specific for rotator cuff; two others are for arm and shoulder.

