4.2 Exclusion criteria

Patients fulfilling any of the following criteria are not eligible for inclusion in this study. No additional exclusions may be applied by the investigator, in order to ensure that the study population will be representative of all eligible patients.

1. Use of other investigational drugs at the time of enrollment, or within 5 half-lives of enrollment, or within 30 days for small molecules/until the expected PD effect has returned to baseline for biologics, whichever is longer; or longer if required by local regulations.
2. History of hypersensitivity to any of the study treatments or excipients or to drugs of similar chemical classes
3. Rheumatologic, inflammatory diseases, including but not limited to: PsA, AS and RA
4. Previous shoulder surgery in affected shoulder

5. History of adhesive capsulitis/frozen shoulder or calcification in the tendon (in affected or contralateral shoulder) confirmed by X-Ray, historic X-Rays can be used if performed within 3 months of baseline
6. Symptomatic osteoarthritis of the shoulder (gleno-humeral, acromioclavicular) (in affected or contralateral shoulder confirmed by X-Ray, historic X-Rays can be used if performed within 3 months of baseline)
7. Neck conditions, including but not limited to cervical spine syndrome, which in the opinion of the investigator, may explain the patient's symptoms
8. Previous platelet rich plasma injections within the last 12 months prior to randomization
9. Previous treatment with any cell-depleting therapies including but not limited to anti-CD20, investigational agents (e.g. Campath, anti-CD4, anti-CD5, anti-CD3, anti-CD19)
10. Previous exposure to any biologic immunomodulating agents, including but not limited to TNFalpha inhibitors (including, but not limited to adalimumab, infliximab), or biologics targeting IL-17 (including, but not limited to secukinumab, ixekizumab or brodalumab) or the IL-17 receptor within the last 12 months prior to baseline
11. Patients taking high-potency opioid analgesics, including but not limited to, methadone, hydromorphone, and morphine
12. Any intraarticular/subacromial corticosteroid treatment within 8 weeks prior to randomization and more than 3 injections for the current tendinopathy. Oral, intramuscular or i.v. corticosteroid treatment within the last 12 months prior to randomization

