6.10 Concomitant treatment

The investigator must instruct the subject to notify the study site about any new medications he/she takes after the subject has been enrolled into the study.

All prescription medications, over-the-counter drugs and significant non-drug therapies (including physical therapy and blood transfusions) administered or taken within the timeframe defined in the entry criteria prior to the start of the study and during the study, must be recorded on the Concomitant medications/Significant non-drug therapies CRF.

Medication entries should be specific to trade name, the single dose and unit, the frequency and route of administration, the start and discontinuation date and the reason for therapy.

Each concomitant drug must be individually assessed against all exclusion criteria/prohibited medication. If in doubt, the investigator should contact Novartis before randomizing a subject or, if the subject is already enrolled, to determine if the subject should continue participation in the study.

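### Exclusion criterion 10's 12-month look-back, read naturally, conflicts with Table 5-1 and with the IL-17-naïve rule in Section 3.2, and Table 5-1's intramuscular steroid washout contradicts criterion 12

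*Protocol*

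**What the plan says.** **Biologics.** Criterion 10 in Protocol Section 4.2 opens with "Previous exposure to any biologic immunomodulating agents, including but not limited to TNFalpha inhibitors". It goes on to biologics against IL-17, naming secukinumab among others, and ends "or the IL-17 receptor within the last 12 months prior to baseline".

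The first row of Table 5-1 in Section 5.1 covers "Any immunomodulating biologic drugs, including but not limited to TNFalpha inhibitors or other biologic drugs targeting IL-17 or IL-17 receptor" and is marked 'Never'. Footnote 1 explains the term: "Never = medication is prohibited from any time point prior to study start and up to and including follow-up visit". Section 3.2, describing who may enter, says "Patients must be naïve to IL-17 inhibition therapy".

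The neighbouring criterion 9 bars "Previous treatment with any cell-depleting therapies including but not limited to anti-CD20" with no time limit. Its row in Table 5-1 is also 'Never', so there the two places agree.

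**Intramuscular steroid.** Criterion 12 excludes oral, intramuscular and intravenous corticosteroid use in the 12 months before randomization. Table 5-1 has a systemic corticosteroid row at 12 months and a separate intramuscular row at 8 weeks.

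**Precedence.** Section 4.2 tells investigators, at its start and again at its end, not to add exclusions of their own, and Section 4 says much the same. Neither the protocol nor the SAP says which text prevails when Section 4.2 and Table 5-1 differ.

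**The concern.** These are operative rules that sites use to decide who enters, and for biologics they give different answers. A site that follows Section 4.2 literally, as it is told to, could enrol a patient whom Table 5-1 and Section 3.2 both rule out.

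The IL-17 agents matter most. IL-17A blockade is the mechanism under test, and immunogenicity in secukinumab-treated patients is a secondary objective with a Day 1 sample (Section 2.2). Earlier exposure to the study drug or to its class bears on what the trial measures.

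For intramuscular steroid the stake is smaller. A site working from the table row could accept a patient whom criterion 12 excludes, which would be an avoidable entry deviation.

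**Working it through.** No stated figure needs reproducing. The check sets the rules side by side and runs test patients through them.

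**Inputs**
- Criterion 10: 12 months, counted back from baseline. On the natural reading, the closing time phrase limits the whole list, because the criterion is one sentence governed by one idea, previous exposure.
- Table 5-1, biologics row: no look-back limit.
- Section 3.2: no look-back limit, but only for IL-17 inhibition.
- Criterion 9 and its Table 5-1 row: no look-back limit in either.
- Criterion 12, intramuscular steroid: 12 months (about 52 weeks) before randomization.
- Table 5-1: intramuscular row 8 weeks, systemic row 12 months, local shoulder injection row 8 weeks. All are counted from randomization.

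**Test patients**

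| Last exposure | Section 4.2 | Table 5-1 | Section 3.2 |
|---|---|---|---|
| Secukinumab, 18 months before baseline | Passes criterion 10 (18 > 12) | Barred | Barred |
| Adalimumab, 18 months before baseline | Passes criterion 10 (18 > 12) | Barred | Not addressed |
| Cell-depleting therapy, 18 months before baseline | Barred by criterion 9 | Barred | Not addressed |
| Intramuscular steroid, 20 weeks before randomization | Barred by criterion 12 (20 < 52) | Satisfies the intramuscular row (20 > 8) | Not addressed |

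**Reasoning**
1. Row 1 is a three-way comparison in which criterion 10 is the outlier: two separate provisions set no time limit on IL-17 exposure, and one sets 12 months.
2. Row 2 is a two-way conflict. Section 3.2 does not speak to TNF-alpha inhibitors, so nothing shows whether 12 months or 'Never' was intended.
3. Row 3 shows that the plan has a consistent form available. The mismatch belongs to criterion 10 and is not a general difference between Section 4.2 and the table.
4. In row 4 the two windows differ by 52 − 8 = 44 weeks, approximately. Criterion 12 rejects everyone in that gap, so the added eligibility is 0 weeks. The local injection row (8 weeks) and the systemic row (12 months) both agree with criterion 12; only the intramuscular row does not.

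**The case against.** **Section 4.2 decides entry, and Table 5-1 is about conduct.** Section 5 is framed as restrictions during the study, most of the table's actions are to stop study medication, and some rows (conventional DMARDs, retinoids) have no matching exclusion. On this view criterion 10 stands and the 'Never' footnote is loose. This is a fair account of precedence, and it is why the intramuscular cell does no harm to eligibility. It does not remove the biologics conflict. The footnote expressly reaches back before study start, and Section 3.2 describes entry. If criterion 10 does govern, it is the laxer rule, and it admits patients whom the other two texts bar.

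**The 12-month phrase may attach only to part of the list.** A reader might infer that a conflict survives however the sentence is parsed. The documents do not support that. If the phrase limits only the last item, the opening words carry no time limit and already bar every biologic immunomodulator, including those against the IL-17 receptor. The closing phrase is then redundant or odd, and a patient exposed to a receptor agent need not pass criterion 10. The conflict is therefore claimed on the natural reading only.

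**Sites can ask.** Section 6.10 says "If in doubt, the investigator should contact Novartis before randomizing a subject". This limits the harm. A reader might go further and note that the same section asks for earlier medication only "within the timeframe defined in the entry criteria prior to the start of the study", and conclude that older biologic exposure would go unrecorded. That does not follow: Section 8.5.4 has drugs given before the start of treatment entered on the prior and concomitant medications page with no look-back limit, and Section 8.5 collects general medical history.

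**The remedy assumes intent.** For biologics other than IL-17 agents this is right, and the fix leaves the choice of window to the sponsor.

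**Conclusion.** The point holds on the natural reading of criterion 10. That criterion conflicts with Table 5-1 for all the biologics it lists, and with Section 3.2 for agents that inhibit IL-17. The intramuscular cell in Table 5-1 is wrong against both criterion 12 and the table's own systemic row, but it makes nobody eligible who was not already.

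The documents give no number of affected patients. It is probably very small, since criterion 3 removes patients with PsA, AS and RA. A reader might infer that plaque psoriasis patients form a sizeable exposed group because psoriasis is not named there. The documents do not show that: criterion 3 is an open list, and Section 3.1 describes a population without systemic inflammatory disease. Counting the drug classes in conflict would say nothing about how many patients are affected.

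The endpoint, analysis model, sample size, power and alpha are unaffected. This is a minor correction, worth making because it concerns rules that sites must apply.

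**What to change.** 1. In criterion 10, remove the 12-month limit for agents targeting IL-17 or its receptor, using the unlimited form of criterion 9. This brings it into line with Table 5-1 and Section 3.2.
2. For other biologics, such as TNF-alpha inhibitors, choose either 12 months or never and state it identically in criterion 10 and Table 5-1. If 12 months is chosen, split the first row of the table so that 'Never' stays for IL-17 and IL-17 receptor agents.
3. Set the intramuscular steroid row of Table 5-1 to 12 months, or merge it into the systemic corticosteroid row.

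The cost is protocol wording, made through the amendment route in Section 13.1, with no added visits or procedures. The downside is that a probably very small number of previously exposed patients become ineligible. Choosing 12 months for the other biologics keeps patients with older TNF-inhibitor exposure eligible. The steroid change excludes nobody whom criterion 12 does not already exclude.

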6.1 Study treatment

Details on the requirements for storage and management of study treatment, and instructions to be followed for subject numbering, prescribing/dispensing and taking study treatment are outlined in the SOM.

6.1.1 Investigational and control drug(s)

Table 6-1 Overview of study medication

Study drug name	Formulation	Unit dose	Packaging	Provided by
Secukinumab 300 mg (2 injections of 150 mg)	2 x 1 mL PFS	1 mL (150 mg)	Single -blind supply	Novartis
Placebo, 2 injections	2 x 1 mL PFS		Single-blind supply	Novartis

Patients will be given the injections by the site staff on site, except for injections at weeks 1 and 3, which will be given by a study nurse on site or at home, whichever is most convenient for the patient, in agreement with the investigator.

The PFSs are packed in a single blinded fashion and do not need to be prepared. The study treatments will be labeled as follows:

- Single blind secukinumab and placebo pre-filled syringe (PFS) will be labeled AIN457 150 mg/1 ml/Placebo for dosing up to and including Week 12.

For detailed instructions on storage of the investigational treatments, please refer to the SOM.

6.1.2 Additional study treatment

No additional treatment beyond investigational drug and control drug are included in this trial.

6.2 Treatment arms

Patients will be assigned to one of the following 2 treatment arms in a 1:1 ratio, with approximately 50 patients per arm.

- Group 1: Secukinumab 300 mg s.c. (2 x 150 mg)
- Group 2: Placebo s.c. (2 injections)

Treatment is administered at Day 1 (randomization visit), and Weeks 1, 2, 3, 4, 8 and 12.

Subjects who complete the assessments associated with Week 14 visit should continue the study in a (treatment free) follow up period of 10 weeks up to 24 weeks.

6.3 Treatment assignment and randomization

The randomization numbers will be generated using the following procedure to ensure that treatment assignment is unbiased and concealed from subjects and investigator staff. A subject randomization list will be produced by the Interactive Response Technology (IRT) provider using a validated system that automates the random assignment of subject numbers to randomization numbers. These randomization numbers are linked to the different treatment arms, which in turn are linked to medication numbers. A separate medication list will be produced by or under the responsibility of Novartis Drug Supply Management using a validated system that automates the random assignment of medication numbers to packs containing the investigational drug(s).

The randomization number is only used to identify which treatment the subjects have been randomized to receive. The Subject number assigned to a subject at screening remains the unique identifier for the subject throughout the study. For information on subject numbering, please see 'Subject numbering' section in the SOM.

Randomization will be stratified on the basis of

- Tendinopathy without tear / tendinopathy with partial tear.
- Steroid-naïve for the current RC injury / local steroid treatment for the current RC injury.

The stratification occurs in order to make sure that these two potential factors, which may impact response to treatment, are evenly distributed in the treatment groups.

The randomization scheme for subjects will be reviewed and approved by a member of the Randomization Office.

Follow the details outlined in the Site Operations Manual regarding the process and timing of treatment assignment and randomization of subjects.

6.4 Treatment blinding

This is a subject, investigator and sponsor-blinded study. Subjects, investigators and sponsor will remain blinded to study treatment throughout the study, except where indicated below.

The identity of the treatments will be concealed by the use of study drugs that are all identical in packaging, labeling, schedule of administration, appearance, and odor.

Site staff

All site staff (including study investigator and study nurse), except the unblinded pharmacist, will be blinded to study treatment throughout the study.

Unblinding a single subject at site for safety reasons (necessary for subject management) will occur via an emergency system in place at the site (see [Section 6.6](#)).

Sponsor staff

All other sponsor staff (study statistician, study programmer, biomarker expert, clinical trial team, decision boards etc.) will stay blinded to treatment assignments (except in the case of a safety event necessitating unblinding) until after database lock for the analysis of the primary endpoint at Week 14. Study monitors will remain blinded throughout the study.

All unblinded personnel will otherwise keep randomization lists and data or information that could unblind other study team members confidential and secure until database lock for the primary endpoint at Week 14.

Following final database lock all roles may be considered unblinded. See [Table 6-2](#) for an overview of the blinding/unblinding plan.

The sample analysts will receive a copy of the randomization schedule (via request to the Randomization Office), to facilitate analysis of the samples. The sample analysts will provide the sample data to the study team under blinded conditions unless otherwise allowed.

The study statistician will be able to access the randomization list for interim analyses and is allowed to share unblinded information with the rest of the clinical team as appropriate for internal decision purposes, as outlined in [Table 6-2](#). For example, unblinded summaries and unblinded individual data can be shared with the team for after the primary endpoint analysis at Week 14.

Study programmers and other personnel involved in study data analysis (e.g. biomarker expert) are allowed to access treatment assignment information for the purpose of conducting the primary endpoint analysis.

The clinical trial team is allowed to share unblinded results with other sponsor staff (e.g. decision boards) as required for internal decision making on the study or the project at the time of interim analyses while the study is ongoing.

Table 6-2 **Blinding and unblinding plan**

Role	Time or Event			
	Randomization list generated	Treatment allocation & dosing	Safety event (single subject unblinded)	Primary analysis at Week 14
Subjects/Patients	B	B	UI	B
Site staff	B	B	UI	B
Unblinded pharmacist	B	UI	UI	UI
Drug Supply and Randomization Office	UI	UI	UI	UI
Statistician/statistical programmer/ data analysts (e.g. biomarker, PK)	UI	UI	UI	UI
Unblinded monitor	B	UI	UI	UI
All other sponsor staff not identified above (trial team, project team, management & decision boards, support functions)	B	B	UI	UI

Key:

UI: Allowed to be unblinded on individual patient level

B: Remains blinded

NA: Not applicable to this study

6.5 Treating the subject

AIN457 will be administered to the subject via the s.c. route of administration. Patients will be given the injections by the site staff on site, except for injections at weeks 1 and 3, which will be given by a study nurse on site or by a study nurse at home, whichever is most convenient for the patient. See the Site Operations Manual for further details.

Sponsor qualified medical personnel will be readily available to advise on trial related medical questions or problems.

6.5.1 Instructions for prescribing and taking study treatment

Study treatment (2 x 150 mg s.c. secukinumab or matching placebo) will be administered by PFSs throughout the study.

S.c. administration with pre-filled syringes

Secukinumab solution for s.c. injection (150 mg in 1.0 mL active/placebo) will be provided in PFSs. Details of the injection is provided in the SOM. Permitted dose adjustments and interruptions of study treatment

Study treatment interruption should be avoided with the following exceptions:

Study treatment interruption is only permitted if, in the opinion of the investigator, a subject is deemed to be placed at a significant safety risk unless dosing is temporarily interrupted. In such cases study treatment should be interrupted only during the time that this risk is present and ongoing. Study treatment can be restarted at the next scheduled visit after resolution of the safety risk.

Any study treatment interruption must be recorded on the corresponding eCRF page.

